8.3.3.1 Relationship to Study Drug

All adverse events (AEs) must have their relationship to study drug assessed by the clinician who examines and evaluates the participant based on temporal relationship and his/her clinical judgment. The degree of certainty about causality will be graded using the categories below. In a clinical trial, the study product must always be suspect.

- **Definitely Related:** There is clear evidence to suggest a causal relationship, and other possible contributing factors can be ruled out. The clinical event, including an abnormal

laboratory test result, occurs in a plausible time relationship to study drug administration and cannot be explained by concurrent disease or other drugs or chemicals. The response to withdrawal of the study drug (dechallenge) should be clinically plausible. The event must be pharmacologically or phenomenologically definitive, with use of a satisfactory rechallenge procedure if necessary.

- **Probably Related:** There is evidence to suggest a causal relationship, and the influence of other factors is unlikely. The clinical event, including an abnormal laboratory test result, occurs within a reasonable time after administration of the study drug, is unlikely to be attributed to concurrent disease or other drugs or chemicals, and follows a clinically reasonable response on withdrawal (dechallenge). Rechallenge information is not required to fulfill this definition.
- **Potentially Related:** There is some evidence to suggest a causal relationship (e.g., the event occurred within a reasonable time after administration of the trial medication). However, other factors may have contributed to the event (e.g., the participant's clinical condition, other concomitant events). Although an AE may rate only as "possibly related" soon after discovery, it can be flagged as requiring more information and later be upgraded to "probably related" or "definitely related", as appropriate.
- **Unlikely to be related:** A clinical event, including an abnormal laboratory test result, whose temporal relationship to study drug administration makes a causal relationship improbable (e.g., the event did not occur within a reasonable time after administration of the study drug) and in which other drugs or chemicals or underlying disease provides plausible explanations (e.g., the participant's clinical condition, other concomitant treatments).
- **Not Related:** The AE is completely independent of study drug administration, and/or evidence exists that the event is definitely related to another etiology. There must be an alternative, definitive etiology documented by the clinician.

As a guide, some questions to ask/think about when addressing drug-related causality may include:

- Is the AE a known reaction of the drug?
- Is the AE similar to other adverse events listed the investigator's brochure or consent documents?
- Has the AE occurred before in this study?
- Is the AE reasonably temporally related to the drug?
- Does the AE improve or disappear when the drug is discontinued? What happens on re-test?
- Was the AE present at the baseline assessment of the study participant or in the study participant's recent medical history?
- Can the AE be reasonably explained by the study participant's clinical disease status?
- Are there any other potential causes for the AE?

8.3.3.2 *Expectedness*

An unexpected adverse event is one where the nature or intensity is not consistent with the information in the Investigator's Brochure (for compounds in development) or the USPI (for compounds marketed in the US).

Furthermore, reports which add significant information on specificity or so far unexpected severity of a known, already documented adverse reaction constitute unexpected events. For example, an event more specific or more severe than described in the USPI or Investigator's Brochure would be considered 'unexpected'.

Expectedness will be assessed by the CRO Medical Monitor and Sponsor.

8.3.4 Time Period and Frequency for Event Assessment and Follow-up

The occurrence of an adverse event (AE) or serious adverse event (SAE) may come to the attention of study personnel during study visits and interviews of a study participant presenting for medical care, or upon review by a study monitor.

All AEs including local and systemic reactions not meeting the criteria for SAEs will be captured on the appropriate case report form (CRF). Information to be collected includes event description, time of onset, clinician's assessment of severity, relationship to study product (assessed only by those with the training and authority to make a diagnosis), and time of resolution/stabilization of the event. All AEs occurring while on study must be documented appropriately regardless of relationship. All AEs will be followed to adequate resolution.

Any medical condition that is present at the time that the participant is screened will be considered as baseline and not reported as an AE. However, if the study participant's condition deteriorates at any time during the study, it will be recorded as an AE.

Changes in the severity of an AE will be documented to allow an assessment of the duration of the event at each level of severity to be performed. AEs characterized as intermittent require documentation of onset and duration of each episode.

PI will record all reportable events with start dates occurring any time after informed consent is obtained until 7 (for non-serious AEs) or 30 days (for SAEs) after the last day of study participation. A follow-up call at day 7 or day 30 will be conducted to confirm resolution or stabilization of adverse events. At each study visit, the investigator will inquire about the occurrence of AE/SAEs since the last visit. Events will be followed for outcome information until resolution or stabilization.

Any adverse event or abnormal laboratory result considered clinically relevant will be followed until it reaches a satisfactory resolution, becomes stable, or can be explained by other causes (e.g., concurrent condition or medication), and clinical judgment indicates that further evaluation is not warranted. All findings must be reported in the study participant's file.

8.3.5 Adverse Event Reporting

Adverse events reported spontaneously by site staff outside the above indicated time points will also be documented.

The occurrence of all adverse events will be documented in the electronic Case Report Form with the following information where appropriate:

- Nature of adverse event (reported adverse event term)
- When the adverse event first occurred (onset)
- When the adverse event ended and/or how long it persisted
- Whether the adverse event was serious
- Intensity of the adverse event
- Concomitant medications
- Concomitant procedures
- Definite or last observed outcome
- Relationship to IMPs

8.3.6 Serious Adverse Event Reporting

The study clinician will immediately report (within 24 hours) to the CRO any serious adverse event, whether or not considered study drug related, including those listed in the protocol or investigator brochure and must include an assessment of whether there is a reasonable possibility that the study drug caused the event. Study endpoints that are serious adverse events (e.g., all-cause mortality) must be reported in accordance with the protocol unless there is evidence suggesting a causal relationship between the study drug and the event (e.g., death from anaphylaxis). In that case, the investigator must immediately report the event to the CRO.

All serious adverse events (SAEs) will be followed until satisfactory resolution or until the site investigator deems the event to be chronic or the participant is stable. Other supporting documentation of the event may be requested by the Data Coordinating Center (DCC)/study Sponsor and should be provided as soon as possible.

The CRO will be responsible for notifying the Food and Drug Administration (FDA) of any unexpected fatal or life-threatening suspected adverse reaction as soon as possible, but in no case later than 7 calendar days after the CRO's initial receipt of the information. In addition, the Sponsor must notify FDA and all participating investigators in an Investigational New Drug (IND) safety report of potential serious risks, from clinical trials or any other source, as soon as possible, but in no case later than 15 calendar days after the CRO determines that the information qualifies for reporting.

8.3.7 Reporting Events to Parents/Legal Guardians

Not applicable.

8.3.8 Events of Special Interest

8.3.8.1 *Cardiovascular Events*

The following events will be considered serious adverse events:

- Systemic Hypertension (must require treatment)
- Major venous or arterial thrombosis (clot)
- Disseminated Intravascular Coagulation (DIC)
- Pulmonary Hypertension
- Intracranial Hemorrhage
- Cardiopulmonary Arrest

8.3.8.2 *Laboratory Investigations*

The following events will be considered serious adverse events:

- Polycythemia

8.3.8.3 *Serious Dermatological Reactions*

Serious and sometimes fatal post-marketing cases of dermatologic reactions, including Stevens-Johnson syndrome (SJS) and Toxic Epidermal Necrolysis (TEN) have been reported in patients treated with phenobarbital. Post-marketing reporting rate is generally accepted to be an underestimate due to under-reporting. Recurrence of serious skin reactions following rechallenge with phenobarbital has also been reported. Therefore, if a study participant develops a skin reaction during phenobarbital treatment, consideration should be given to permanent discontinuation and replacement of the drug with alternative treatment.

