2.2.1 Clinical

In infants with seizures, phenobarbital 15–20 mg loading dose with additional 5–10 mg/kg doses to maximal plasma concentration of 40 mg/L (172 micromol/L) resulted in a plateau of the response rate. Plasma concentrations >50 mg/L (215 micromol/L) were associated with sedation and feeding difficulty (9).

The clearance of phenobarbital increases with birth weight and postnatal age, but is reduced at a concentration >50 mg/L (215 micromol/L) (10). Bioavailability is 50% after oral administration. Simulations recommend a loading dose 20 mg/kg and maintenance 2.5 – 5 mg/kg/day for intravenous administration and; loading dose 40 mg/kg and maintenance 5 – 11 mg/kg/day for oral administration to meet a target phenobarbital concentration between 15 and 30 mg/L (64.5 and 129.1 micromol/L) (11). The clinical management of neonatal seizures and the doses (both partial and cumulative) of phenobarbital administered as first line therapy have generally varied among clinicians and institutions. A total dose of 50 mg/kg can be given if required (12).

The clearance may also be reduced in infants with perinatal asphyxia undergoing therapeutic hypothermia (13-15). In term infants treated with hypothermia, an initial phenobarbital loading dose of 20 mg/kg with an additional 10–20 mg/kg if needed is recommended (15).

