2.3.1.4 Adverse Reactions

Expected phenobarbital adverse reactions include drowsiness, lethargy, impaired sucking reflex and poor feeding. If administration is too rapid, expected adverse reactions include respiratory depression, apnea, hypotension, laryngospasm and bronchospasm. Other expected adverse reactions include phlebitis, tissue necrosis if extravasation occurs, GI intolerance, physical dependence and tolerance, folate deficiency, hepatitis and hypocalcaemia.

Stevens-Johnson syndrome and Toxic Epidermal Necrolysis: Serious and sometimes fatal dermatologic reactions, including Stevens-Johnson syndrome (SJS) and Toxic Epidermal Necrolysis (TEN) have been reported with phenobarbital. Post-marketing reporting rate is generally accepted to be an underestimate due to under-reporting. Recurrence of serious skin reactions following re- challenge with phenobarbital has also been reported. Therefore, if a study participant develops a skin reaction during phenobarbital treatment, consideration should be given to permanent discontinuation and replacement of the drug with alternative treatment.

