3.7.2. Secondary outcomes

Efficacy

- Percent of neonates who do not require additional seizure treatment after 2 hours of the first dose of phenobarbital.

CONFIDENTIAL

- Percent of neonates who do not require additional seizure treatment after the second dose of phenobarbital within the first 24 hours of treatment.
- Seizure burden over 24 hours following initial administration of the phenobarbital injection.
- Seizure burden over 48 hours following initial administration of the phenobarbital injection.
- Percent of neonates requiring alternative anticonvulsive therapy for the management of seizures at 24 and 48 hours.
- Time period between the first dose and second dose of intravenous phenobarbital in neonates randomized.
- Time period between the second dose of intravenous phenobarbital and alternative anticonvulsant treatment in neonates
- Time period between the first dose of intravenous phenobarbital and administration of an alternative anticonvulsant treatment in neonates randomized.

Safety

The following safety assessments will be performed during the study:

- Type, incidence, and severity of adverse events
- Physical examination
- Vital signs (blood pressure [arterial line], respiration rate, pulse rate, oxygen saturation and temperature)
- Clinical laboratory tests (hematology, serum chemistry)

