8.2. Vital Signs

Vital sign data including blood pressure (BP), heart rate, respiratory rate and body temperature will be listed for individual subjects.

Vital sign data, along with changes from baseline will be summarized separately, overall and by treatment using descriptive statistics. For each vital sign variable, baseline value will be calculated as the last value prior to dosing.

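### Safety dose-response is part of the primary objective, but no by-arm estimate is planned for the respiratory, hypotensive and sedative reactions that the protocol expects from phenobarbital

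*Protocol*

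**What the plan says.** **Objective.** Protocol 3.1.1 and SAP 2.1 make the primary objective a dose-response of two doses for both safety and efficacy.

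**Expected reactions.** Protocol 2.3.1.4 lists drowsiness, lethargy, impaired sucking and poor feeding without condition. It then adds a conditional group: "If administration is too rapid, expected adverse reactions include respiratory depression, apnea, hypotension, laryngospasm and bronchospasm". Protocol 2.2.1 reports that plasma concentrations above 50 mg/L "were associated with sedation and feeding difficulty".

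**Special-interest list.** Protocol 8.3.8 has three parts. The cardiovascular part begins with "Systemic Hypertension (must require treatment" and continues with thrombosis, DIC, pulmonary hypertension, intracranial hemorrhage and cardiopulmonary arrest. The laboratory part has one item, "Polycythemia". Both parts are introduced by "The following events will be considered serious adverse events". The third part covers serious skin reactions.

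**Analysis.** Protocol 9.4.4 and SAP 8.1 plan numbers and percentages of neonates with treatment-emergent events by system organ class and preferred term, with separate summaries of serious events and discontinuations. The SAP never mentions events of special interest.

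**Vital signs.** SAP 3.7.2, like protocol 3.2.4, includes oxygen saturation among the safety endpoints: "Vital signs (blood pressure [arterial line], respiration rate, pulse rate, oxygen saturation and temperature". The SAP section that analyses them reads: "Vital sign data including blood pressure (BP), heart rate, respiratory rate and body temperature will be listed for individual subjects".

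**The concern.** If a trial sets out to compare the safety of two doses, one expects the plan to say on which events the doses will be compared and by what estimate. Here the protocol identifies the drug's likely reactions, but nothing in the analysis follows from that.

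At stake is the safety half of the primary objective. Without groups fixed in advance, the final report will hold tables of individual terms, and any pooling of related terms will be chosen after the results are known. A reader could then neither trust a reported excess at the higher dose nor take comfort from its absence.

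**Working it through.** The point has no figure of its own in the documents. The check sets the passages side by side, with a little arithmetic.

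**1. Number per arm (plan's own figure).** Protocol 9.2: 70% vs 50%, alpha 0.05, 80% power. Two-sided, pooled variance:

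n = [1.960·√(2·0.60·0.40) + 0.8416·√(0.70·0.30 + 0.50·0.50)]² / 0.20² = (1.3579 + 0.5708)² / 0.04 = 93 per group.

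Total 186; 186/0.95 = 195.8, so 196 randomised, or 98 per arm. The plan's numbers reproduce and are not in question.

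**2. Could the arms differ on these reactions?**
- *Rate.* The synopsis and protocol 4.1 give the same 30-minute infusion to both arms. First dose: 20/30 = 0.67 and 40/30 = 1.33 mg/kg/min, a ratio of 2. The documents do not say what counts as too rapid, so this does not show that either rate is. It shows that the arms differ on the very condition to which 2.3.1.4 ties the respiratory and hypotensive reactions.
- *Exposure.* Regimen maxima are 20 + 20 = 40 and 40 + 10 = 50 mg/kg. Protocol 4.3 cites a serum goal of about 50 µg/mL (= 50 mg/L) or a 24-hour total of 50 mg/kg. These are alternative limits, not a predicted concentration, but 50 mg/L is also the level above which 2.2.1 reports sedation and feeding difficulty.

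**3. Expected reactions against the plan.**

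| Protocol 2.2.1 / 2.3.1.4 | Named in 8.3.8? | Grouped by-arm estimate in SAP? |
|---|---|---|
| Respiratory depression, apnea | No (cardiopulmonary arrest is) | No |
| Laryngospasm, bronchospasm | No | No |
| Hypotension | No (treated hypertension is) | No |
| Drowsiness, lethargy, sedation, poor feeding | No | No |
| Stevens-Johnson syndrome / TEN | Yes | No |

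**4. What the SAP 8.1 tables can show.** The class rows pool some related terms, but neither class nor term rows give the number of neonates with a given reaction group:
- The reactions fall in different classes. The protocol's Appendix III has separate respiratory, nervous-system and vascular classes.
- A class row mixes drug reactions with illness. Appendix III puts bronchospasm beside asphyxia and pulmonary haemorrhage, and protocol 7.4.1.2 expects asphyxia-related events in this population.
- Each row counts neonates with at least one event, so a neonate with two terms appears in two rows. The rows cannot be added.

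**5. Precision that the fix would give (illustration only).** The documents give no toxicity rates. Assume a common rate p in both arms with 98 per arm; the 95% half-width of the risk difference is 1.96·√(2p(1−p)/98):

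| Assumed p | Half-width |
|---|---|
| 5% | 6.1 points |
| 10% | 8.4 points |
| 20% | 11.2 points |
| 30% | 12.8 points |

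The intervals would be wide, but they would state what the trial can and cannot exclude.

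**The case against.** **The list drives no analysis.** A reader might infer that 8.3.8 aims the safety comparison at the wrong events. The documents do not support that. For the cardiovascular and laboratory items its stated function is to set seriousness, and the safety analysis rests on all treatment-emergent events. A list that confers automatic SAE status need not include common expected reactions. The list also is not empty of drug toxicity: it covers serious skin reactions ("Serious and sometimes fatal post-marketing cases of dermatologic reactions, including Stevens-Johnson syndrome (SJS) and Toxic Epidermal Necrolysis (TEN"), and cardiopulmonary arrest would catch the extreme of respiratory depression. Appendix III flags bronchospasm, acute respiratory failure and respiratory arrest for seriousness. This objection stands.

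**The reactions are already followed.** Protocol 1.3 records vital signs before each dose, every 15 ± 5 minutes to one hour after each infusion, then every 4-6 hours. SAP 8.2 summarises change from baseline by treatment. This stands for data collection. As analysis it is thin: no threshold, lowest value or between-arm interval is planned. Alertness and sucking are in the neurologic examination (8.2.5), but 1.3 schedules that only at screening and at the end of follow-up or discharge.

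**SAP 8.2 is not exhaustive.** Its list is introduced as inclusive and SAP 3.7.2 names oxygen saturation, so this is a gap in wording. It is still worth closing for a drug with expected respiratory effects.

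**Two further inferences fail.** One might think that an intracranial hemorrhage that is the entry diagnosis becomes an automatic SAE; protocol 8.3.4 already treats conditions present at screening as baseline unless they worsen. One might also think that the DSMB could miss an excess; the DSMB sees unblinded data (7.4.1.2) and its criteria are in a charter that was not available, so nothing can be concluded.

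**Conclusion.** The point holds as a gap in the analysis plan. Safety dose-response is in the primary objective, the protocol names the reactions to expect, the arms differ twofold in first-dose rate, and no grouped by-arm estimate of those reactions is pre-specified. The safety comparison is aimed at no particular events, which is different from being aimed at the wrong ones.

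Its size is modest. No sample size or stated figure changes, and the events will be in the database. The loss cannot be quantified: power figures would rest on assumed toxicity rates and describe a test that the plan does not contain. The conclusion rests on the protocol and SAP alone; if the DSMB charter or another document already defines such groups, the remedy is to bring them into the SAP.

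**What to change.** 1. **SAP 8.1.** Before unblinding, define three MedDRA preferred-term groups: (a) respiratory depression, apnea, laryngospasm, bronchospasm; (b) hypotension; (c) sedation and poor feeding. The sponsor sets the definitions. For each, report the number of neonates with at least one event by arm, and the risk difference (high minus low dose) with its 95% CI, in the safety population. Use an interval method suited to small counts.
2. **Protocol 8.3.8.** Name these groups as events of special interest that are not automatically serious, and state the basis for the existing list.
3. **SAP 8.2.** Add oxygen saturation and summarise each neonate's lowest recorded post-dose value by arm. Because a second dose brings extra readings, also report it for the period up to 30 minutes after the first infusion ends, the earliest time that a second dose is allowed, when both arms follow the same schedule.

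**Cost.** Some SAP wording, term selection and programming, plus a short protocol edit. The data are already collected; no dose, treatment rule or sample size changes. Intervals will be wide for rare events, and the estimates should be presented as descriptive.

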8.3.9 Reporting of Pregnancy

Not Applicable

8.4 Unanticipated Problems

8.4.1 Definition of Unanticipated Problems (UP)

Sponsor considers unanticipated problems involving risks to participants or others to include, in general, any incident, experience, or outcome that meets all of the following criteria:

- Unexpected in terms of nature, severity, or frequency given (a) the research procedures that are described in the protocol-related documents, such as the Institutional Review Board (IRB)-approved research protocol and informed consent document; and (b) the characteristics of the participant population being studied;
- Related or possibly related to participation in the research (“possibly related” means there is a reasonable possibility that the incident, experience, or outcome may have been caused by the procedures involved in the research); and

- Suggests that the research places participants or others at a greater risk of harm (including physical, psychological, economic, or social harm) than was previously known or recognized.

